#### 6. DOSING DELAYS/DOSE MODIFICATIONS

#### 6.1 Recommended Ixazomib Criteria for Beginning or Delaying a Subsequent Treatment Cycle & Dose Modifications for Treatment Associated Toxicity

For a new cycle of treatment to begin during induction, the patient must meet the following criteria:

- ANC must be  $\geq 1,000/\mu$ L.
- Platelet count must be  $\geq 75,000/\mu$ L.
- All other clinically significant, study drug related non hematologic toxicity must have resolved to ≤ Grade 1 or to baseline condition

If the participant fails to meet the above-cited criteria for initiation of a new cycle of treatment during induction, dosing will be delayed for 1 week. At the end of that time, the participant should be re-evaluated to determine whether the above criteria have been met. If the participant continues to fail to meet the above-cited criteria, delay therapy and continue to re-evaluate. The maximum delay for toxicity before treatment is permanently discontinued will be 3 weeks, however delays due to other circumstances should be discussed with the Principal Investigator. Delays of > 3 weeks must be discussed with the Principal Investigator. Re-treatment will be at the discretion of the Principal Investigator.

During maintenance, the above pre-treatment criteria must only be met every 3 months during cycles when a provider is seen. During cycles when the patient does not return to clinic, sites must follow local guidelines for pre-treatment criteria.

There is no specific pre-treatment criteria for lenalidomide during induction or maintenance. Sites should follow local guidelines for beginning a new cycle of treatment with lenalidomide.

If any one of the study medications is permanently discontinued for toxicity, the patient may remain on the study at the discretion of the investigator.

| Dose Level    | Dose        |
|---------------|-------------|
| Starting Dose | 4.0 mg      |
| -1            | 3.0 mg      |
| -2            | 2.3 mg      |
| -3            | Discontinue |

#### Table 10: Ixazomib Dose Adjustments

If ixazomib is reduced for any toxicity, the dose may not be re-escalated.

A delay of up to 14 days will be allowed for participants for non-AE related events (i.e.; vacation, family emergency, etc) after discussion with the overall PI.

For both Ixazomib and lenalidomide the investigator may discuss considerations for dose modifications and symptom management with the Principal Investigator.

#### Treatment modifications due to Ixazomib or lenalidomide-related AEs are outlined in Tables **11 and 12**.

| I able 11: Ixazomib and Lenalidomide Dose Adjustments for Hematologic Toxicities
Within-Cycle Dose Modifications (other than Day 1)                        |  |  |  |  |  |
|---|--|--|--|--|--|
| Criteria  | Action   |  |  |  |  |
| Platelet count ≤ 30,000/µL  | 
 
Ixazomib dose should be held. Lenalidomide dose should be held.
 
Complete blood count (CBC) with differential should be repeated at least every other day until the ANC and/or platelet counts have exceeded the pre-specified values on at least 2 occasions.
 
   |  |  |  |  |
| or
ANC ≤ 500/µL  | • Upon recovery (1 st occurrence), lenalidomide may be reinitiated with 1 dose level reduction depending on the attribution of the toxicity to the study agent. Do not dose reduce ixazomib. Upon recurrence of the toxicity (2 nd occurrence), ixazomib may be reinitiated with 1 dose level reduction depending on the attribution of the toxicity to the study agent.   |  |  |  |  |
| Dose Modifications  | for Subsequent Treatment Cycles on Day 1   |  |  |  |  |
| Criteria  | Action   |  |  |  |  |
| Delay of > 2 weeks in the start of a
subsequent cycle due to lack of
toxicity recovery as defined in
Section 6.3.1
ANC < 1,000/µL
Platelet count < 75,000/µL | 
 
Hold ixazomib and lenalidomide until resolution as per criteria Section 6.1.
 
Upon recovery, reduce lenalidomide 1 dose level, depending on the attribution of the toxicity to the study agent. If lenalidomide has been reduced during the cycle, consider a dose reduction of ixazomib upon reinitiating the subsequent cycle.
 
The maximum delay before treatment should be discontinued will be 3 weeks or at the discretion of the PI.
 
  |  |  |  |  |
| Dose Modifica   | tions for Subsequent Treatment Cycles  |  |  |  |  |
| Criteria  | Action   |  |  |  |  |
| All Hematologic Toxicities  | 
 
For any hematologic toxicity that occurs during a cycle but recovers in time for the start of the next cycle:
 
If dose was reduced within the cycle, start the next cycle at that same dose.
 
If due to toxicity timing, ie, after Day 15 dosing thus a dose reduction was not required at that point in the cycle, reduce ixazomib by 1 dose level at the start of that cycle.
 
Do not reduce the dose both within a cycle and at the start of the cycle for the same most severe toxicity.
 
 |  |  |  |  |

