- **Thrombocytopenia.** Blood counts will be monitored regularly as outlined in the protocol with additional testing obtained according to standard clinical practice. Thrombocytopenia may be severe but has been manageable with platelet transfusions according to standard clinical practice. Ixazomib administration should be modified as noted as per dose modification recommendations in the protocol when thrombocytopenia occurs (see Section 6.1). Therapy can be reinitiated at a reduced level upon recovery of platelet counts. A rare risk is thrombotic thrombocytopenic purpura (TTP), a rare blood disorder where blood clots form in small blood vessels throughout the body characterized by thrombocytopenia, petechiae, fever, or possibly more serious signs and symptoms. TTP should be managed symptomatically according to standard medical practice.
- **Neutropenia.** Blood counts will be monitored regularly as outlined in the protocol with additional testing obtained according to standard clinical practice. Neutropenia may be severe but has been manageable. Growth factor support is not required but may be considered according to standard clinical practice. Ixazomib administration should be modified as noted as per dose modification recommendations in the protocol when neutropenia occurs (see Section 6.1). Therapy can be reinitiated at a reduced level upon recovery of ANCs.
- Fluid Deficit. Dehydration should be avoided since ixazomib may cause vomiting, diarrhea, and dehydration. Acute renal failure has been reported in patients treated with ixazomib, commonly in the setting of the previously noted gastrointestinal toxicities and dehydration.
  - Fluid deficit should be corrected before initiation of study drug and as needed during treatment to avoid dehydration.

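### Table 11 gives incompatible ixazomib instructions for a first hematologic event after Day 15 dosing, and Section 6.1 and Table 11 disagree on whether lenalidomide has Day 1 count criteria

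*Combined protocol and SAP*

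**What the plan says.** **Ixazomib.** The within-cycle row of Table 11 applies when platelets are ≤ 30,000/µL or ANC is ≤ 500/µL. Both drugs are held. On recovery from a first occurrence, lenalidomide may restart one level lower, subject to attribution, and for the other drug the row says "Do not dose reduce ixazomib". Only at the second occurrence does the row mention lowering ixazomib: "ixazomib may be reinitiated with 1 dose level reduction depending on the attribution of the toxicity to the study agent".

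The last row of the table, headed for all hematologic toxicities, opens with this scope: "For any hematologic toxicity that occurs during a cycle but recovers in time for the start of the next cycle". Where the event came too late for a reduction within the cycle, with after Day 15 dosing given as the case, it says "reduce ixazomib by 1 dose level at the start of that cycle".

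**Lenalidomide.** The text of Section 6.1 states: "There is no specific pre-treatment criteria for lenalidomide during induction or maintenance". It then sends sites to local guidelines. The Day 1 row of Table 11 lists a delay of more than 2 weeks, ANC < 1,000/µL and platelets < 75,000/µL, and gives the action "Hold ixazomib and lenalidomide until resolution as per criteria Section 6.1".

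**Permanence.** Sections 6.1 and 6.2 do not allow either drug to be re-escalated after a reduction for toxicity. The notes to Table 8 start maintenance at the reduced dose if ixazomib fell below 4 mg in induction, or if lenalidomide fell below 15 mg.

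**The concern.** These are operating instructions for a multi-site trial. Where two of them cover the same patient on the same day and differ, each site must choose one. Patients with identical events could then leave the episode on different doses. Because reductions are one-way, the difference lasts.

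Two things are at stake. One is consistent handling of hematologic toxicity. The other is interpretation: in a single-arm trial, the 2-year progression-free rate is meant to describe one regimen, and the regimen delivered would depend partly on which line of the table a site followed.

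**Working it through.** There is no sample-size or power figure to reproduce. The check sets the rules side by side on test cases and then works out how long a divergence would last.

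**Case 1: a first platelet count ≤ 30,000/µL after the Day 15 ixazomib dose, recovered by the next Day 1.**
- Within-cycle row: this is a first occurrence, so "Do not dose reduce ixazomib".
- Last row: this is a hematologic toxicity that recovered in time and came after Day 15 dosing, so ixazomib goes down one level.
- Ixazomib is given on Days 1, 8 and 15, so its next dose is Day 1 of the next cycle. Both rows govern that dose. Under Table 10, a patient at the starting dose would take 4.0 mg on one row and 3.0 mg on the other.

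**Case 2: the same first event earlier in the cycle.** The within-cycle row leaves ixazomib unreduced, and the last row's instruction for late events is not triggered. The rows agree, so the ixazomib conflict is confined to Case 1.

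**Case 3: platelets below 75,000/µL on Day 1 of a later induction cycle.**
- Section 6.1 text: no protocol criterion for lenalidomide; local guidelines decide.
- Table 11, Day 1 row: lenalidomide is held with ixazomib until the Section 6.1 criteria (ANC ≥ 1,000/µL, platelets ≥ 75,000/µL) are met.
- The table as extracted does not show whether the counts are triggers in their own right or only describe a delay of more than 2 weeks. On the first reading the conflict arises on any such Day 1. On the second it arises only after a prolonged delay. Either way, lenalidomide is tied to counts that the text says do not govern it.
- The row defines recovery by reference to Section 6.3.1. No such section exists; Section 6.3 covers dexamethasone.

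**Duration of an ixazomib divergence.** Maintenance is Cycles 10 to 24, so 24 − 9 = 15 cycles, and 15/24 = 62.5% of planned cycles. If the event falls in Cycle 1, the lower level could apply from Cycle 2: 8 induction cycles + 15 = 23 of 24. One level down from the starting dose is (4.0 − 3.0)/4.0 = 25%.

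**Duration of a lenalidomide divergence.** Table 13 steps through 25, 20, 15, 10 and 5 mg. One or two reductions leave 20 or 15 mg, neither below 15 mg, so maintenance still starts at 15 mg. It takes three (10 mg) before the Table 8 note applies.

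**Number of patients.** Two sets of rates in the protocol might be tried:
- Drug-related grade 3 or higher events in the newly diagnosed myeloma study of this combination (Section 2.7.2): neutropenia 56 × 8/65 = 6.9; thrombocytopenia 56 × 5/65 = 4.3.
- All-grade events in the pooled oral combination studies (Table 6): neutropenia 56 × 43/173 = 13.9; thrombocytopenia 56 × 49/173 = 15.9.

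The answers run from about 4 to about 16, and neither set uses Table 11's thresholds. In the first, 15 of the 65 patients came from a phase 1 part with escalating ixazomib doses. Neither gives the share of first events that fall after Day 15 dosing and recover in time. No count follows.

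**The case against.** **The last row can be read narrowly.** It explains that a reduction was not required at that point because of timing. It could therefore be limited to events for which an ixazomib reduction was otherwise due, which would exclude first occurrences. The same row also bars reducing both within a cycle and at the start of the next for one toxicity, so a lenalidomide reduction already made might be thought to rule out one for ixazomib. Both readings are possible, but neither is written down. The row's scope is any hematologic toxicity, the reason it gives is timing rather than occurrence number, and the bar on double reduction does not say whether it works across drugs.

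**The lenalidomide row may be a rule for prolonged delay rather than an entry test.** This is fair and lowers the certainty about how often the conflict arises, but it does not remove it. Nor can Table 11 be set aside as an ixazomib table. Its title names both drugs, Section 5.2.2.1 sends lenalidomide delays to Sections 6.1 and 6.2, and Section 6.2 points back to Tables 11 and 12.

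**Investigators may discuss dose changes with the Principal Investigator.** Section 6.1 allows this for both drugs, and it should reduce variation between sites. It is optional and does not settle which row governs.

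**Section 5.4 is not a further contradiction.** A reader might infer one from "Therapy can be reinitiated at a reduced level upon recovery of platelet counts". That sentence permits rather than orders a reduction, and the one before it defers to the dose rules in Section 6.1. A site can follow both.

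**Conclusion.** Two conflicts stand on the current text: ixazomib after a first event that follows Day 15 dosing and recovers by the next cycle, and lenalidomide at the start of a cycle when counts are low. A dead cross-reference in the Day 1 row adds to the second. The ixazomib conflict is a direct opposition in one table. The lenalidomide conflict is firm in substance, but its trigger is uncertain because of the extracted layout.

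The consequence for an individual can be long: up to 15 maintenance cycles for ixazomib, plus any induction cycles remaining after the reduction. For lenalidomide it reaches the maintenance dose only when the induction dose has fallen below 15 mg.

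A reader might infer three stronger conclusions that the documents do not support:
- That every first event is caught. Earlier first events get consistent ixazomib instructions.
- That about 7 and 4 of 56 patients are affected. Those figures rest on rates that match neither the thresholds nor the timing.
- That the 2-year rate is biased by some stated amount. Section 13.1.1 keeps every treated patient in the analysis, and nothing in the protocol links these dose differences to progression. What can be said is that the delivered regimen would be less uniform.

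This is an internal inconsistency that should be corrected because the instructions are incompatible and reductions are irreversible. The conclusion assumes that the rows are read as written, without limits that the text does not state.

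**What to change.** The sponsor should amend Section 6.1 and Table 11 together:
- Reconcile the within-cycle row with the row for all hematologic toxicities, so that a first event after Day 15 dosing has one instruction for each drug. Say explicitly whether the last row depends on occurrence number and whether the bar on double reduction applies per drug or across drugs.
- Reconcile the Section 6.1 statement on lenalidomide with the Day 1 row. State whether the Day 1 counts apply to lenalidomide, and whether they act alone or only with a delay of more than 2 weeks.
- Replace the Section 6.3.1 reference with the section intended.
- Send sites a clarification memo with the amendment.

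The cost is amendment wording and one memo; sample size, endpoints and visits do not change. The choice of rule belongs to the sponsor, and this review does not say which is right.

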### Table 11: Ixazomib and Lenalidomide Dose Adjustments for Hematologic Toxicities

| Adverse Event   | Severity  | Action on Study Drug  | Further Considerations  |
|---|---|---|---|
|   | Grade 1
Peripheral
Neuropathy                               | No action   | Grade 1 signs and symptoms:
asymptomatic; without pain or
loss of function; clinical or
diagnostic observations only
deep tendon reflexes or
parasthesia |
| New or
Worsening
Peripheral
Neuropathy | Grade 1
Peripheral
Neuropathy
with pain
or
Grade 2 | Hold Ixazomib until resolution to Grade $\leq 1$ without pain or baseline   | Grade 2 signs and symptoms:
Moderate symptoms; limiting
instrumental activities of daily
living (ADL)  |
| (CTCAE v.4.0)   | Grade 2
Peripheral
Neuropathy
with pain
or
Grade 3 | Hold Ixazomib until
resolution to Grade ≤ 1
without pain or baseline
Reduce study drug to next
lower dose upon recovery   | Grade 3 signs and symptoms:
severe symptoms; limiting
self-care ADL; assistive
device indicated  |
|   | Grade 4
Peripheral
Neuropathy                               | Discontinue Ixazomib  | Grade 4 signs and symptoms:
Life threatening
consequences; urgent
intervention indicated   |
| Rash  | Grade 2   | Symptomatic
recommendations as per
section 5.3 and 5.4  |   |
| Non-Hematologic   |   | Hold Ixazomib or
lenalidomide depending on
the attribution until
resolution to Grade < 1 or
baseline  |   |
| toxicities judged
to be related to
study drug                         | Grade 3   | If not recovered to < Grade
1 or baseline within 3
weeks:
Reduce Ixazomib or
lenalidomide depending on
the attribution to next
lower dose upon return to
< Grade 1 or baseline | Symptomatic
recommendations noted in
Section 5.3 and 5.4  |

#### Table 12: Ixazomib and Lenalidomide Dose Adjustments for Non-Hematologic Toxicities

If the patient discontinues either Ixazomib or lenalidomide, he or she does not need to come off protocol therapy.

#### If ixazomib is reduced for any toxicity, the dose may not be re-escalated.

#### 6.2 Lenalidomide

See dose modifications described above in tables 11 and 12.

#### Table 13: Lenalidomide Dose Reduction

| Dose Level | Lenalidomide Dose |
|------------|-------------------|
| 0          | 25 mg             |
| -1         | 20 mg             |
| -2         | 15 mg             |
| -3         | 10 mg             |
| -4         | 5 mg              |

#### If lenalidomide is reduced for any toxicity, the dose may not be re-escalated.

#### 6.3 Dexamethasone

|   | Dose Modificati   |   |
|---|---|---|
|   | Gast  | rointestinal  |
| Dyspepsia   | Grade 1-2   | Treat with H2 blockers, sucralfate, or omeprazole.
If symptoms persist despite above measures,
decrease dexamethasone by 1 dose level   |
| Gastric or
Duodenal Ulcer
Gastritis   | ≥ Grade 3
(requiring
hospitalization
or surgery) | Hold dexamethasone until symptoms adequate
controlled. Restart and decrease 1 dose level of
current dose along with concurrent therapy with
H2 blockers, sucralfate, or omeprazole. If
symptoms persist despite above measures, |
|   |   | discontinue dexamethasone and do not resume.  |
| Acute Pancreatitis  | All Grades  | Discontinue dexamethasone and do not resume.  |
|   | Care  | diovascular   |
| Edema   |   | Diuretics as needed, and decrease dexamethasone dose by 1 dose level;   |
| (limiting function and
unresponsive to therapy or
anasarca)   | $\geq$ Grade 3  | If edema persists despite above measures, decrease
dose another level and do not resume if symptoms
persist despite second reduction.   |
|   | N   | eurology  |
| Confusion or Mood
Alterations
(interfering with function
+/- interfering with
estimities of daily living)   | $\geq$ Grade 2  | Hold dexamethasone until symptoms resolve.
Restart with 1 dose level reductions.
If symptoms persist despite above measures,
discontinue dexamethasone and do not resume.  |
| activities of daily living)   |   |   |
|   | Muse  | culoskeletal  |
| Muscle Weakness
(symptomatic and
interfering with function
+/- interfering with
activities of daily living) | ≥ Grade 2   | Decrease dexamethasone 1 dose lever.
If weakness persists despite above measures
decrease by 1 dose level.
Discontinue dexamethasone and do not resume if
symptoms persist.   |
|   | N   | letabolic   |
| Hyperglycemia   | ≥ Grade 3   | Treatment with insulin or oral hypoglycemics as
needed.
If uncontrolled despite above measures, decrease
dose level by 1 dose level until levels are
satisfactory.  |

#### Table 14: Dexamethasone Dose Modifications

If the patient discontinues dexamethasone, he or she does not need to come off protocol therapy.

| Table 15: | Dexamethasone | dose reduction |
|-----------|---------------|----------------|
|-----------|---------------|----------------|

| Dose Level | Dexamethasone Dose |
|------------|--------------------|
| 0          | 40 mg              |
| -1         | 20 mg              |
| -2         | 10 mg              |

If dexamethasone is reduced for any toxicity, the dose may not be re-escalated.

#### 7. ADVERSE EVENTS: LIST AND REPORTING REQUIREMENTS

#### 7.1 Definitions

#### Adverse Event Definition

Adverse event (AE) means any untoward medical occurrence in a patient or subject administered a pharmaceutical product; the untoward medical occurrence does not necessarily have a causal relationship with this treatment. An AE can therefore be any unfavorable and unintended sign (including an abnormal laboratory finding), symptom, or disease temporally associated with the use of a medicinal (investigational) product whether or not it is related to the medicinal product. This includes any newly occurring event, or a previous condition that has increased in severity or frequency since the administration of study drug. **CTCAE version 4.03** will be used for this study.

An abnormal laboratory value will not be assessed as an AE unless that value leads to discontinuation or delay in treatment, dose modification, therapeutic intervention, or is considered by the investigator to be a clinically significant change from baseline.

#### **Serious Adverse Event Definition**

Serious AE (SAE) means any untoward medical occurrence that at any dose:

- Results in death.
- Is life-threatening (refers to an AE in which the patient was at risk of death at the time of the event. It does not refer to an event which hypothetically might have caused death if it were more severe).
- Requires inpatient **hospitalization or prolongation of an existing hospitalization** (see clarification in the paragraph below on planned hospitalizations).
- Results in **persistent or significant disability or incapacity**. (Disability is defined as a substantial disruption of a person's ability to conduct normal life functions).

- Is a congenital anomaly/birth defect.
- Is a **medically important event**. This refers to an AE that may not result in death, be immediately life threatening, or require hospitalization, but may be considered serious when, based on appropriate medical judgment, may jeopardize the patient, require medical or surgical intervention to prevent one of the outcomes listed above, or involves suspected transmission via a medicinal product of an infectious agent. Examples of such medical events include allergic bronchospasm requiring intensive treatment in an emergency room or at home, blood dyscrasias or convulsions that do not result in inpatient hospitalization, or the development of drug dependency or drug abuse: any organism, virus, or infectious particle (eg. prion protein transmitting Transmissible Spongiform Encephalopathy), pathogenic or nonpathogenic, is considered an infectious agent.

Clarification should be made between a serious AE (SAE) and an AE that is considered severe in intensity (Grade 3 or 4), because the terms serious and severe are NOT synonymous. The general term severe is often used to describe the intensity (severity) of a specific event; the event itself, however, may be of relatively minor medical significance (such as a Grade 3 headache). This is NOT the same as the serious, which is based on patient/event outcome or action, criteria described above, and is usually associated with events that pose a threat to a patient's life or ability to function. A severe AE (Grade 3 or 4) does not necessarily need to be considered serious. For example, a white blood cell count of 1000/µL to less than 2000 is considered Grade 3 (severe) but may not be considered serious. Seriousness (not intensity) serves as a guide for defining regulatory reporting obligations.

Adverse event (AE) monitoring and reporting is a routine part of every clinical trial. The following list of reported and/or potential AEs (Section 7.2) and the characteristics of an observed AE (Section 7.3) will determine whether the event requires expedited reporting in addition to routine reporting.

